6.3.2 Exclusion Criteria

The presence of any of the following excludes a subject from study enrollment:

1. History of anaphylaxis or Type 1 hypersensitivity reaction to agalsidase alfa or agalsidase beta
2. History of renal dialysis or transplantation
3. Linear negative slope of eGFR of ≥ 2 mL/min/1.73 m² based on at least 4 serum creatinine values over approximately 2 years (including the value obtained at the screening visit)
4. History of acute kidney injury in the 12 months prior to screening, including specific kidney diseases (e.g., acute interstitial nephritis, acute glomerular and vasculitic renal diseases); non-specific conditions (e.g., ischemia, toxic injury); as well as extrarenal pathology (e.g., prerenal azotemia, and acute post renal obstructive nephropathy)
5. Angiotensin converting enzyme (ACE) inhibitor or angiotensin receptor blocker (ARB) therapy initiated or dose changed in the 4 weeks prior to screening
6. Urine protein to creatinine ratio (UPCR) at screening > 0.5 g/g or mg/mg or 500 mg/g and not treated with an ACE inhibitor or ARB
7. Females who are pregnant, planning to become pregnant during the study, or are breast feeding
8. Cardiovascular event (myocardial infarction, unstable angina) in the 6-month period before screening
9. Cerebrovascular event (stroke, transient ischemic attack) in the 6-month period before screening
10. Presence of any medical, emotional, behavioral, or psychological condition that, in the judgment of the Investigator and/or Medical Director, would interfere with the patient's compliance with the requirements of the study.

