8.3.1 Adverse Events

An adverse event (AE) is any untoward medical occurrence in a subject participating in a clinical trial. An AE can be any unfavorable and unintended sign, symptom, or disease temporally associated with the use of the study medication, whether or not considered related to the study medication. AEs will be collected from the start of treatment until 30 days following the final visit dose. If the subject enters the extension study, the first 30 days of the extension study will be considered the observation period for adverse events of this study (PB-102-F50). Any events occurring prior to treatment will be recorded on the medical history page with the event name and onset date and end date if not continuing. Known pre-existing clinically significant conditions observed at screening should be recorded as medical history.

This definition also includes accidental injuries, reasons for any change in medication (drug and/or dose) other than planned titration, reasons for admission to a hospital, or reasons for surgical procedures (unless for minor elective surgery for a pre-existing condition). It also includes AEs commonly observed and AEs anticipated based on the pharmacological effect of the study medication. Any laboratory abnormality assessed as clinically significant by the Investigator must be recorded as an AE.

A treatment-emergent AE is any AE occurring after start of study medication and within the time of residual drug effect (30 days after the last administration of the study medication; please note the above provision for subjects who enter the extension study), or a pre-treatment AE or pre-existing medical condition that worsens in intensity after start of study medication and within the time of residual drug effect.

AEs should be recorded as diagnoses, if available. If not, separate sign(s) and symptom(s) are recorded. One diagnosis/symptom should be entered per record. Treatment-related hypersensitivity/infusion reactions are defined in [Appendix 3. Pegunigalsidase alfa Hypersensitivity Evaluation and Treatment Algorithm](#) and can be defined as a single AE at the Investigator's discretion.

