### **7.2.2 Partial or Missing Dates of Episodes of Acute Kidney Injury**

Episodes of Acute Kidney Injury (AKI) are reported by the investigators as AE. An AKI episode is defined between the start and the end date of the AKI AE. The following rules will be followed in case on incomplete start or end date of an AKI event:

- AKI start date:
  - If month and year are available and day is missing, the 1st of the month will be imputed. In case the event is during the month of the first infusion, it will be imputed to the date of 1st infusion.
  - If month is missing and year is available then if the year is the same as the year of 1st infusion then the date should be the date of 1st infusion. Otherwise the date should be set to January 1st.
  - If year is missing then the date should be imputed to date of 1st infusion.

- AKI end date:
  - If month and year are available and day is missing, the last day of the month will be imputed. In case the event is during the month of the last infusion, it will be imputed to the date of end of study.
  - If month is missing and year is available then if the year is the same as the year of last infusion then the date should be the last day in the study. Otherwise the date should be set to December 31st.
  - If year is missing then the date should be imputed to last day in the study.

Serum creatinine during episodes of acute kidney injury (AKI) will be excluded from the eGFR slope calculation and summary tables and considered to be missing.

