### 9.1 eGFR

eGFR will be calculated based on the value of the serum creatinine values according to the CKD-EPI formula:

$$\text{eGFR (mL/min/1.73 m}^2\text{)} = 141 \times \min(\text{Scr}/\kappa, 1)^\alpha \times \max(\text{Scr}/\kappa, 1)^{-1.209} \times 0.993^{\text{Age}} \\ \times 1.018 \text{ [if female]} \times 1.159 \text{ [if black / African American]}$$

where Scr is serum creatinine (mg/dL),  $\kappa$  is 0.7 for females and 0.9 for males,  $\alpha$  is -0.329 for females and -0.411 for males, min indicates the minimum of  $\text{Scr}/\kappa$  or 1, and max indicates the maximum of  $\text{Scr}/\kappa$  or 1.

Serum creatinine can be recorded in two units,  $\mu\text{mol/L}$  and  $\text{mg/dL}$ . In calculation of eGFR or summary of creatinine, the value in  $\mu\text{mol/L}$  needs to be converted to  $\text{mg/dL}$  using the following conversion formula:  $1 \text{ mg/dL} = 88.4 \mu\text{mol/L}$ .

The age should be the actual age when the subject's serum creatinine is collected. The calendar age at each timepoint should be used in the formula to be consistent with that in the Electronic Data Capture system.

The results of the serum creatinine test at the screening visit appears twice in the database: once as part of the data transferred from the central laboratory and once in the eCRF (once the site receives from the central laboratory, the value is entered into the eCRF to check the eligibility in terms of eGFR value and the eGFR slope). These two values should be identical. In the listings, by-visit tables of eGFR and slope calculations, the value entered to eCRF should be used.

Episodes of Acute Kidney Injury (AKI) are reported by the investigators as AE (The associated System Organ Class (SOC) is Renal and urinary Disorders and Preferred Term (PT) is Acute Kidney Injury. Serum creatinine measurements, if any, during an AKI episode will be excluded from the eGFR summary tables and any analysis related

to eGFR. An AKI episode is defined between the start and the end date of the AKI AE. The imputation of date in case of a partial dates are provided in Section 7.2.

eGFR values during an AKI episode will only be listed.

eGFR will be summarized descriptively by visit overall.

A shift from baseline to Week 52 or early termination, between the following eGFR categories will be presented:

- $eGFR \geq 90 \text{ mL/min/1.73 m}^2$ ,
- $60 \text{ mL/min/1.73 m}^2 \leq eGFR < 90 \text{ mL/min/1.73 m}^2$ ,

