## 9.2 eGFR Slope

For each patient, the following linear regression using all the available eGFR values after, and including, the baseline visit will be used to compute the eGFR slope after the switch to PRX-102:

$$eGFR = \alpha + \beta \times [\text{time in year}]$$

The slope  $\beta$  ( $\text{mL/min/1.73 m}^2 / \text{year}$ ) will be an estimate of the subject's annualized change in eGFR. The “[time in year]” in the formula is the time, in year, from “baseline” to the respective visit, and will be estimated by  $(\text{date of the visit} - \text{date of baseline})/365.25$ . In case of study prolongation due to COVID-19, only data collected up to Week 52 (Visit 14) will contribute to the slope calculation. In case of switching dosing regimen, the slope calculations will be based on eGFR measured up to (including) the visit of the switch.

The slope prior to the switch will be calculated in a similar manner, using the historical serum creatinine values as well as screening and the baseline serum creatinine value. Any eGFR data obtained more than 730 days (approximately 24 months) prior to Screening visit will not be used in estimating the pre-switch annualized slope.

The screening slope which is based on the historical serum creatinine values as well as screening serum creatinine, and is documented in the eCRF.

The serum creatinine at baseline is used in the two slopes calculations (pre- and post-switch).

Note that the resulting slope will include the baseline serum creatinine which is not used for the evaluation of inclusion/exclusion. It may be that the slope with the baseline (prior to the switch) will be different from the slope at screening.

The eGFR slopes pre and post switch as well as the screening slope will be summarized descriptively. The summary of the slope post switch will include also a 95% Confidence Interval (CI) for the mean slope based on a t-distribution.

This analysis will be repeated for all the subgroups defined in Section 7.5.

For the sub-groups, a 95% CI, for the mean difference in slope post switch between the two categories within each sub-group, will be constructed based on t-distribution.

The sub-groups will be summarized graphically by box-plots.

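### Creatinine drawn during an AKI 12 to 24 months before screening stays in the pre-switch eGFR slope, while creatinine during a reported AKI on PRX-102 is removed from the post-switch slope

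*SAP*

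**What the plan says.** **Exclusion rule.** SAP 7.2.2: "Serum creatinine during episodes of acute kidney injury (AKI) will be excluded from the eGFR slope calculation and summary tables and considered to be missing". SAP 9.1 gives the same rule a wide scope: "Serum creatinine measurements, if any, during an AKI episode will be excluded from the eGFR summary tables and any analysis related" to eGFR. Neither section separates pre-switch from post-switch data.

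**What counts as an episode.** SAP 7.2.2: "An AKI episode is defined between the start and the end date of the AKI AE". SAP 9.1 repeats this definition.

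**When AEs are collected.** Protocol 8.3.1: "AEs will be collected from the start of treatment until 30 days following the final visit dose". Earlier events go elsewhere: "Any events occurring prior to treatment will be recorded on the medical history page with the event name and onset date and end date".

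**Eligibility.** Protocol 6.3.2, criterion 4, excludes "History of acute kidney injury in the 12 months prior to screening".

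**Slopes.** SAP 9.2 computes the pre-switch slope "using the historical serum creatinine values as well as screening and the baseline serum creatinine value", going back as far as 730 days before screening. The post-switch slope uses eGFR from baseline onward. Pre-switch, post-switch and screening slopes are all summarised descriptively. Of the three overall means, only the post-switch one is given a confidence interval.

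**The concern.** The exclusion is worded as if it covers every eGFR analysis, but its trigger is an adverse event record. An AKI that ended before the first infusion has no such record under the protocol, so the rule finds nothing to exclude in the historical data. SAP 9.2 says the pre-switch slope is calculated in a similar way to the post-switch one. That does not help, because the definition carried over still depends on an AE.

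The trial has no control arm, so readers will set the post-switch slope beside the pre-switch one. If one has AKI values removed and the other does not, part of any difference comes from the rule. Few points are required before the switch (at least three historical values, plus screening and baseline), so a single depressed value can move a patient's slope a long way.

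**Working it through.** The documents state no figure to reproduce: the sample size is pragmatic and no AKI frequency is given. The check has two parts, coverage of the window and an illustration of size.

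**1. Coverage**
- Window before screening: 730 days (SAP 9.2).
- Barred by exclusion 4: the latest 12 months, 365 days.
- Neither barred nor cleaned: 730 − 365 = 365 days, or 50%, which is months 12 to 24.
- The interval from screening to first dose (about 30 days) is unclear. The protocol treats events there as medical history, while SAP 10.2.1 has a pre-treatment AE category.

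**2. Effect of one AKI value on eGFR**
- Protocol 8.3.4 sets the AKI threshold at a 1.5-fold creatinine rise.
- Above κ, CKD-EPI eGFR varies as Scr^−1.209, so the fall is 1 − 1.5^−1.209 = 0.388, or 39%. It is smaller if the usual creatinine lies below κ, and larger if the rise exceeds 1.5-fold.

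**3. Weight of each value in the slope**
- Assumed layout: historical values 24, 16 and 8 months before screening, then screening, then Visit 1 about a month later.
- Times in years from Visit 1: −2.08, −1.41, −0.75, −0.08, 0; mean −0.864.
- Deviations: −1.216, −0.546, 0.114, 0.784, 0.864; sum of squares 3.151.
- Least-squares weight = deviation / 3.151, giving −0.386, −0.173, +0.036, +0.249, +0.274 per year.

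**4. Shift in one patient's pre-switch slope** = |weight| × 0.388 × usual eGFR, upward for the two early points

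| AKI value is | eGFR 50 | eGFR 80 | eGFR 100 |
|---|---|---|---|
| earliest point | +7.5 | +12.0 | +15 |
| second point | +3.4 | +5.4 | +6.7 |

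Dividing by 30, one affected patient raises the mean by about 0.25 to 0.5 (earliest point) or 0.11 to 0.22 (second point).

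**5. Screening slope (no Visit 1 value)**
- The earliest point has weight −0.45, so the shift is 0.45 × 0.388 × 50 = 8.7 up to 0.45 × 0.388 × 100 = 17.5.

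**6. An AKI near month 12**
- With historical values at 22, 17 and 12.5 months, an AKI at 12.5 months and eGFR 80, the pre-switch slope rises by about 2.1. The mean over 30 rises by 2.1 / 30 = 0.07.
- In this layout the screening slope moves slightly the other way (about −0.5). The upward direction therefore holds when the AKI value falls clearly before the average date of that patient's values.

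For scale, exclusion 3 uses a limit of 2 mL/min/1.73 m² on the rate of decline, which the SAP expresses per year.

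**The case against.** The strongest reply is that little rests on this. Efficacy endpoints are exploratory, and no pre/post difference or test is planned. eGFR is also shown by visit and as a shift from baseline. The effect needs an AKI in months 12 to 24, a creatinine drawn during it, and that value entered as historical; the documents give no frequency for any of these. All of this stands, and it limits the point to a descriptive side-by-side reading.

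Four stronger readings are tempting, but the documents do not support them:

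- **The whole pre-switch period is uncleaned.** Exclusion 4 keeps known AKI out of the latest 12 months. An AKI value at screening would also tend to fail the slope criterion: in the layout above, with eGFR 80 and a true slope of 0 to −1.5, it gives a screening slope of about −14 to −15.5.
- **The rule flatters PRX-102.** An early low value improves the pre-switch slope, so the comparison moves against PRX-102. Deleting AKI values on treatment has no fixed direction. At eGFR 80 and a true slope of −1.5, a retained AKI value would give +8.3 at week 4, −2.4 at week 28 and −12.8 at week 52.
- **The early half of the window carries the most leverage.** The two early weights total −0.559 and the three later ones +0.559. Screening and Visit 1 each outweigh the 16-month point. Only the earliest point is extreme.
- **The post-switch slope is fully cleaned.** It is cleaned only of AKI that the investigator reports as an AE. SAP 12, item 6, replaces the independent nephrology review in protocol 10.3.4 with this.

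The pre-treatment AE category in SAP 10.2.1 does not close the gap. It could plausibly cover events between consent and first dose, not those a year or more earlier. The text of SAP 7.1 was not available to me; a rule there covering historical AKI would settle the matter.

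**Conclusion.** The point holds for months 12 to 24 before screening. On the wording available, the same kidney event is left in the slope if it occurred then and removed if it is reported on PRX-102. The resulting error usually makes the pre-switch period look too good. The sizes in the working are conditional on the assumed visit layout, a usual eGFR of 50 to 100 with creatinine above κ, a rise of exactly 1.5-fold and one affected patient in 30. With no affected patient, the error is zero.

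A reader might also infer that a truly declining patient could pass the slope criterion, since the same value enters the screening slope. That is possible arithmetically, but nothing in the documents shows that it happened. Thirty patients have already taken part, so SAP wording cannot change it. The point is worth correcting because the remedy is cheap and uses dates the protocol already asks for. It does not undermine the study's conclusions by itself.

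**What to change.** In SAP 7.2.2 and 9.2:

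1. For the pre-switch period, define an AKI episode from the onset and end dates in the medical history, and exclude historical creatinine inside it from the pre-switch slope.
2. Do not reuse the date imputation in SAP 7.2.2. It sends a missing start year to the first infusion and a missing end year to the last study day, which would place a historical AKI in the treatment period and miss the historical values. A missing month in an earlier year would span 1 January to 31 December, up to half the window. Where the dates cannot place a value inside or outside the episode, show the pre-switch slope with and without that value.
3. Footnote the number of creatinine values excluded in each period. If none is excluded before the switch, the footnote shows it.
4. Report the documented screening slope unchanged, because eligibility has already been decided on it.

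The cost is SAP wording and a check of medical history dates against historical creatinine dates, with no new data. The downside is that a few pre-switch slopes will rest on fewer values: a patient with the minimum of three historical values goes from five points to four when one is removed.

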## 7.2 Missing Data

Imputations of missing data associated with AE severity and relatedness are specified in Section 10.2. Below are imputations rules related to missing or incomplete dates of AE or medication. No other imputations will be made for missing safety or efficacy endpoints.

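### The SAP removes every eGFR value inside a reported AKI episode, however long it lasts, and lists no eGFR output that keeps them, so a lasting loss under an open AKI would be missing from the eGFR results

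*SAP*

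**What the plan says.** SAP 7.2.2 sets the rule: "Serum creatinine during episodes of acute kidney injury (AKI) will be excluded from the eGFR slope calculation and summary tables". Its span is purely a matter of dates: "An AKI episode is defined between the start and the end date of the AKI AE". SAP 9.1 identifies the event from investigator AE reports whose "Preferred Term (PT) is Acute Kidney Injury", widens the exclusion to any eGFR-related analysis, and adds that "eGFR values during an AKI episode will only be listed".

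Every end-date rule in 7.2.2 takes a late date. A missing day becomes month end, or end of study in the month of last infusion. A missing month becomes 31 December, or the last study day in the year of last infusion. For a missing year, "If year is missing then the date should be imputed to last day in the study". The medication rules in 7.2.1 have a branch for ongoing status; the AKI rules have none. SAP 7.2 adds: "No other imputations will be made for missing safety or efficacy endpoints".

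The outputs affected are the by-visit eGFR summary, the category table ("A shift from baseline to Week 52 or early termination, between the following eGFR categories will be presented") and the slope ("The summary of the slope post switch will include also a 95% Confidence Interval (CI) for the mean slope").

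Protocol 10.3.4 already treats AKI episodes as missing for efficacy. However, it has two independent nephrology experts judge, before database lock, whether AKI occurred and whether the values should leave the slope. SAP section 12, item 6, replaces them with AE reporting and the investigator's judgment.

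**The concern.** Whether a value is excluded depends on the outcome being measured. Removing a transient dip is reasonable, because a dip says little about the long-term course. But the rule does not separate a dip from a permanent step down. If the AE is never closed, or its end date is imputed to study end, every later eGFR value goes. The slope then rests on pre-event values only, and the patient has no later by-visit values and no Week 52 value for the shift table. The case-by-case review that could have kept such values in is gone.

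No table in SAP 13.1 or figure in 13.2 is described as keeping the values, and section 12, item 2, says no sensitivity analysis is planned (in explaining why the per-protocol set was removed). A reader of the eGFR tables could not tell how many values were removed for AKI, or whether a move into the lowest eGFR category had disappeared.

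**Working it through.** The plan gives no figure to reproduce: the sample size is pragmatic, and no AKI rate or slope SD is stated. What follows is an illustration.

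**Inputs from the documents**
- 14 planned creatinine values, Visits 1 to 14, 28 days apart (flow chart).
- CKD-EPI exponent -1.209 for creatinine above kappa; per-patient least-squares slope, time in days/365.25 (SAP 9.1, 9.2).
- AKI threshold of a 1.5-fold creatinine rise (Protocol 8.3.4).
- 30 patients (SAP 4.1).

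**Assumptions**: one affected patient; eGFR 80 and flat before the event; a lasting 1.5-fold rise; AKI left open; values free of noise.

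**Size of the fall.** 1.5^-1.209 = 0.612, so 80 becomes 49.0, a fall of 31.0. At eligible ages, eGFR 80 always means creatinine above kappa: even at age 60, eGFR at kappa is 141 × 0.993^60 = 92.5. The true one-year loss on the 30-patient mean is 31.0/30 = 1.03.

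**All-values slope for a step down at Visit k.** In visit units, the sum of squares about the mean is 14 × (14² - 1)/12 = 227.5. The slope is -31.0 × [(15 - k)(k - 1)/2]/227.5 per visit, times 365.25/28 = 13.045 per year.

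| Onset | (15-k)(k-1)/2 | Slope, all values | Values left | Slope, excluded | Difference on mean of 30 |
|---|---|---|---|---|---|
| Visit 2 | 6.5 | -11.6 | 1 | none | 0.39* |
| Visit 5 | 20 | -35.6 | 4 | 0 | 1.19 |
| Visit 7 | 24 | -42.7 | 6 | 0 | 1.42 |
| Visit 8 | 24.5 | -43.5 | 7 | 0 | 1.45 |
| Visit 14 | 6.5 | -11.6 | 13 | 0 | 0.39 |

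*With one value left no slope can be fitted and the patient drops out of the mean. The difference is 0.39 if the patient's underlying slope equals the average of the others.

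The difference varies with onset because a straight line is being fitted to a step. At Visits 5 to 8 the all-values slope overstates the real fall of 31.0; at Visits 2 and 14 it understates it. In the shift table, the move from the 60-90 category to below 60 has no Week 52 value to show it.

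**Other patterns, same patient**
- AE closed, permanent fall from Visit 5, only Visit 5 excluded: -38.0, against -35.6 with all values.
- AE closed, fall of 31 at Visits 5-6 then 15 below the starting level, only Visits 5-6 excluded: -19.2, against -13.5 with all values. Left open, the same patient has slope 0, a difference of 13.5/30 = 0.45 on the mean.
- Transient fall of 31 at Visits 2-4: 0 excluded, -31.0 × (-13.5)/227.5 × 13.045 = +24.0 kept. At Visits 11-13: 0 excluded, -24.0 kept.

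**Date rules on an example calendar** (first infusion 1 February 2019, last visit 31 January 2020, AKI starting 10 July 2019). End year missing: 8 of 14 values dropped. End date given only as 2019: 6 of 14 dropped.

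**Confidence interval.** I do not compare intervals with and without exclusion, because the patient's excluded slope is noise-free here. A slope from 4 visits has standard error SD × 13.045/√5. For an assumed within-patient SD of 3 to 8 this is 17.5 to 46.7 per year, or 0.58 to 1.56 on the mean of 30.

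**The case against.** Five points can be made for the plan as it stands.

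- **The exclusion is not new or hidden.** The protocol already treats AKI as missing for efficacy, the SAP governs where the two differ, and section 12 discloses the loss of the nephrologist review. This stands. The point is the absence of a companion analysis, not an undeclared change.
- **The bias has no fixed direction.** A reader might infer that the rule systematically flatters the slope. The documents do not support that. An AE closed at stability keeps the later values and can steepen the slope, and keeping a transient dip can create a spurious 24 per year of either sign. Protocol 8.3.1.1 follows events until they resolve or are stable, which may prompt closure, although it sets no AE end date.
- **The all-values slope is not the truth.** This also stands, as the Visit 5 to 8 rows show. It is why 1.19 should be read within 0.39 to 1.45 and beside the true 1.03.
- **The loss would still be seen.** A reader might infer that it vanishes from the report. It does not. The AKI stays in the TEAE tables and the values stay in listing 16.2.1. SAP 10.5 summarises serum creatinine and cystatin C with no AKI exclusion (9.1 confines the exclusion to eGFR, although the phrase summary tables in 7.2.2 is looser). The MSSI renal domain scores low GFR, dialysis or transplantation would count as a Fabry clinical event, and the by-visit n would fall. None of these corrects the slope or shift table or says why values are absent.
- **An exploratory, untested endpoint does not need a sensitivity analysis.** This limits the severity. It does not remove the case for a cheap second run, because the slope is reported with a 95% CI.

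**Conclusion.** The point holds in a limited form. All eGFR analyses omit values inside an investigator-dated AKI episode, with no length limit or recovery test and with late imputed end dates, and no listed eGFR output keeps them. A lasting loss under an AKI that is open, or imputed to end late, would therefore be absent from the slope, by-visit and shift results.

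Under the stated assumptions, one such patient makes the 30-patient mean slope differ from the all-values version by 0.39 to 1.45 mL/min/1.73 m2/year, against a true loss of about 1.0. If fewer than two values remain, that patient has no slope at all. The size rests on assumed patient values; the documents give no AKI rate, AKI in the 12 months before screening is an exclusion, and with no AKI the effect is nil. The absence of an all-values run is judged from SAP sections 9, 12 and 13; the text of SAP 7.1 was not available to check.

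This is worth correcting because the correction is cheap. It does not undermine the study's safety conclusions or any test, since none is planned.

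**What to change.** Keep the planned AKI-excluded tables unchanged. Add a supportive run of three of them with all observed eGFR values included: the overall slope (14.2.1.3.1), the by-visit summary (14.2.1.1) and the category shift (14.2.1.2), the last going to the last observed eGFR.

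Footnote the AKI-excluded tables with the number of patients and values removed for AKI, and how many exclusions ran to study end because the AKI was ongoing or had no end date. A sentence in 7.2.2 saying how an ongoing AKI is handled would be a useful clarification.

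The cost is three extra table runs and a footnote, with no new data or reviewers. The all-values slope may be less favourable, or distorted by a transient AKI, so the two versions should be read side by side and neither treated as the corrected answer. If no AKI occurs, the footnote reads zero and the versions agree.
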